# 2.5 Risk-Benefit-Assessment

The major risk of oral anticoagulation is the risk of bleeding. This risk is dose dependent and exceeds (in combination with aspirin) the bleeding risk of aspirin 100 mg/d (alone) by a factor of 2 (ATLAS trial) (13). The bleeding risk is lower than the bleeding risk with Vitamin K dependent anticoagulant drugs, especially in the dose of 5 mg b.i.d. (7). Unfortunately there are no direct comparisons of the bleeding risk between aspirin 100 mg and rivaroxaban5 mg b.i.d. so far in the literature. The results of the COMPASS trial, which is still recruiting will provide further data on this issue.

Since all patients of our planned investigation have a high risk for cardiovascular disease a primary prevention of CV events with aspirin 100 mg is recommended by several guidelines (19) however, this recommendation is not so strong as the indication for aspirin in the case of secondary prevention. In Germany the therapeutic costs for a primary prevention with aspirin 100 mg even in high risk patients are not covered by general health insurance, therefore a lot of patients do not get a prescription of this medication. The inclusion of these patients with a high CV risk but without a major CV event in medical history would offer the possibility to cover high risk patients with a recommended treatment for the duration of the study. To minimize the bleeding risk for the patients we will conduct four safety visits during the treatment of 20 weeks of study medication and will not include patients with an increased risk of bleeding as stated in the exclusion criteria.

In conclusion there is scientific evidence, that patients with a very high cardiovascular risk in a state of primary prevention and with a low risk for bleeding should be treated. The standard recommended treatment today is low dose aspirin, but in our point of view considering the expected advantages of rivaroxaban at a low dose would outweigh the possible increased risk of bleeding.

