## HO: $\Delta$ FBFRiva $\leq \Delta$ FBFASS H1: $\Delta$ FBFRiva $> \Delta$ FBFASS

- Type I error:  $\alpha$  = 0.05, one-tailed t-test for independent samples
- Power: 1-ß = 0.90
- Estimated dropout rate : 25 %
- Minimum of expected clinical relevant difference between the groups in changes of maximal forearm blood flow ( $\Delta$ FBF) = 1.2 ml/100ml with an estimated standard deviation (SD) of  $\sigma$  = 2.4 ml/100ml [Pistrosch, F. et al. Diabetes Care 27: 484-490, 2004]

Sample size should be N = 188 Patients ( $N_{1/2}$  = 94 patients per arm) for a valid number of 141 patients for per protocol analysis. This sample size may also provide enough power for further analyses.

Additionally, the second primary variable is difference of PWV between treatment groups at EOT Extension (after 52 week of treatment). The sample size calculation is based on the following assumptions:

H0: PWVRiva=PWVASS

H1: PWVRiva≠PWVASS

- Type I error:  $\alpha$  = 0.05, t-test for independent samples

- Power: 1-ß = 0.80
- Estimated dropout rate : 20 %
- Minimum of expected clinical relevant difference between the groups in PWV = 0.7 m/s with an estimated standard deviation (SD) of  $\sigma$  = 1.0 m/s

Sample size should be N=80 patients (40 patients per arm) for a valid number of 66 patients for per protocol analysis.

In summary the necessary sample size would be N=188 patients for the study up to week 20 including 80 patients for the extension up to week 52.

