#### 2.3.3 Explorative study objective(s)

Assessment of platelet activation, measurement of mitogenic potential and risk benefit assessment.

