#### 2.4 Sample size calculation

The first primary variable is the change of forearm blood flow with venous occlusion plethysmography ( $\Delta$ FBF) after forearm ischemia after 20 weeks of treatment. The sample size calculation is based on the following assumptions:

- Hypotheses: H0:  $\mu_{\Delta FBF, Riva} \leq \mu_{\Delta FBF, ASS}$ H1:  $\mu_{\Delta FBF, Riva} > \mu_{\Delta FBF, ASS}$
- Application of t-test for independent samples
- Type I error:  $\alpha = 0.05$
- Power: 1-ß = 0.90
- Estimated dropout rate: 25 %
- Minimum of expected clinical relevant difference between the groups in changes of maximal forearm blood flow ( $\Delta$ FBF) = 1.2 ml/100ml with an estimated standard deviation (STD)  $\sigma$  = 2.4 ml/100ml

Sample size should be at least N = 188 Patients (i.e. N/2 = 94 patients per arm) in order to achieve a valid number of 141 patients (per protocol analysis).

Additionally, the second primary variable is the difference of PWV between treatment groups at EOT Extension (after 52 week of treatment). The sample size calculation is based on the following assumptions:

H0: μPWV, Riva = μPWV, ASS

• H1:  $\mu_{PWV, Riva} \neq \mu_{PWV, ASS}$ 

• Type I error:  $\alpha = 0.05$ , t-test for independent samples

• Power: 1-ß = 0.80

Estimated dropout rate: 20 %

• Minimum of expected clinical relevant difference between the groups in PWV = 0.7 m/s with an estimated standard deviation (STD) of  $\sigma$  = 1.0 m/s

Sample size should be N=80 patients (40 patients per arm) to achieve a valid number of 66 patients for per protocol analysis.

In summary the necessary sample size would be N=188 patients for the study up to week 20 including 80 patients for the extension up to week 52.

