#### 6.3 Hypothesis Testing

Unless otherwise specified all hypotheses will be tested at a 5% level of significance against two-sided alternative hypotheses.

Continuous variables will be analyzed by the following test procedures:

First of all the assumption of normally distributed data will be checked with Shapiro-Wilk test by treatment group. If the hypothesis of normally distributed data cannot be rejected for both treatment groups treatments will be compared by an ANCOVA procedure which includes "treatment" as the main factor and "baseline value" as covariate. T-Tests for independent samples will be used to compare groups at baseline.

In the event that the normality assumption is not warranted, data will be log-transformed and normality assumption of the transformed data will be checked by Shapiro-Wilk test. In case of non-rejection of the hypothesis of normally distributed data for both treatment groups, ANCOVA procedure and t-tests as described above will be performed on the basis of log-transformed data.

Point estimates and 95% CI of the difference in (adjusted) mean change from baseline will be provided if data are evaluated on basis of an ANCOVA procedure.

Otherwise Mann-Whitney's-U test on the basis of original data will be applied for comparison of groups at baseline. Mann-Whitney's-U test on the basis of intra-individual differences to baseline will be applied for treatment comparison per visits after baseline. Wilcoxon's signed rank test will be applied to evaluate changes from baseline per treatment group.

Categorical variables with 2 categories will be analyzed using Fisher's exact test (with Yates correction) to compare proportions between treatment groups. Variables with more than 2 categories will be compared by Pearson's Chi-square test. Additionally for each category, the proportions of treatment groups are compared using an (asymptotic) z test. Significant differences in proportions will be flagged, p-values for the z-test will not be shown.

Missing values will not be imputed.

If necessary, modifications of this general procedure will be described in the following sections of chapter 6.

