#### 6.12.4 Bleedings

The results for major, CRNM, minor and total bleeding will be documented. Total bleeding includes any bleeding event (including CRNM, minor and major bleeding). These analyses will be performed on SAF and PPS.

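### Bleeding and adverse events are compared between arms by p-value only; a risk difference and risk ratio with 95% confidence intervals should be added

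*SAP*

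**What the plan says.** SAP 6.3 treats the two kinds of variable differently. Continuous variables analysed by ANCOVA get a point estimate and 95% confidence interval for the difference in adjusted mean change. Two-category variables get Fisher's exact test and variables with more categories get Pearson's chi-square. Only the latter also get a z-test for each category, of which the SAP says: "Significant differences in proportions will be flagged, p-values for the z-test will not be shown". Protocol 9.2 likewise names only tests for categorical measures.

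SAP 6.12.4 says of bleeding only this: "The results for major, CRNM, minor and total bleeding will be documented". Mock tables 7.8.3 (adverse events) and 7.8.4 (bleeding) give N and % in total and by arm, plus one p-value column for the comparison of proportions. By contrast, the tables for compliance (7.4), exposure (7.5), vital signs (7.8.1) and haemoglobin values (7.8.2) have Effect and 95% CI columns. Odds ratio appears in the SAP's abbreviation list, but in no method and no table.

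SAP 2.3.3 includes among the exploratory objectives "measurement of mitogenic potential and risk benefit assessment", without a method. Protocol 2.5 names bleeding as the main risk of oral anticoagulation and adds: "Unfortunately there are no direct comparisons of the bleeding risk between aspirin 100 mg and rivaroxaban5 mg b.i.d. so far in the literature".

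**The concern.** Bleeding is the risk the protocol singles out, and the protocol itself says that no direct evidence on this comparison exists. The useful output is therefore an estimate of the difference with its precision. The plan provides a test instead. A p-value cannot be set against a benefit; a risk difference with its limits can.

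The sample size was set for forearm blood flow and pulse wave velocity, so a non-significant bleeding comparison is likely over a wide range of true risks even if rivaroxaban causes clearly more bleeding. The planned tables would then show two percentages and a p-value above 0.05, and nothing to tell the reader how large an excess the data still allow. At stake is the safety conclusion of the report. The primary efficacy result is not affected.

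**Working it through.** **1. Arm size.** SAP 2.4: "Sample size should be at least N = 188 Patients (i.e. N/2 = 94 patients per arm". Inputs from Protocol 9.1.8: alpha 0.05 with a "one-tailed t-test for independent samples"; "Power: 1-ß = 0.90"; a difference of "1.2 ml/100ml with an estimated standard deviation (SD) of" 2.4 ml/100ml; 25% dropout.

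- Normal approximation: n = 2 × (1.645 + 1.282)² × (2.4/1.2)² = 68.5, so 69 per arm.
- Noncentral t: 70 per arm (power 0.903).
- Dropout: 70/0.75 = 93.3, so 94 per arm and 188 in total; 188 × 0.75 = 141.

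The plan's figures reproduce. Neither sample size calculation uses a bleeding rate or margin. I take 94 per arm as the safety denominator, assuming that every randomised patient is dosed.

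**2. Chance of missing a doubling.** The test is two-sided Fisher at 0.05, as SAP 6.3 sets for two-category variables. The aspirin-arm risk q is an assumption, and the rivaroxaban risk is set to 2q. The miss rate is 1 − Σ P(X = x) P(Y = y) over all pairs (x, y) with Fisher p ≤ 0.05, where X ~ Bin(94, 2q) and Y ~ Bin(94, q), by full enumeration:

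| Aspirin vs rivaroxaban risk (assumed) | Miss rate |
|---|---|
| 1% vs 2% | 99.5% |
| 2% vs 4% | 96.2% |
| 5% vs 10% | 82.4% |
| 10% vs 20% | 58.6% |
| 15% vs 30% | 35.7% |
| 20% vs 40% | 18.1% |

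The uncorrected z-test behind the flags misses somewhat less often: 89.1% at 2% and 51.1% at 10%. SAP 6.12.4 also analyses bleeding in the per-protocol set; with about 70 per arm, Fisher misses 98.2% at 2% and 69.5% at 10%.

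**3. Counts needed for significance.** With 0, 1, 2, 3, 5 or 8 aspirin patients bleeding, the smallest rivaroxaban count giving p ≤ 0.05 is 6, 8, 10, 11, 15 or 19.

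**4. What an interval would add.** Take 10/94 vs 5/94 as an illustration. Fisher gives p = 0.28, and that is all table 7.8.4 would show beyond the percentages.

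- Difference: 0.1064 − 0.0532 = 0.0532.
- Wilson 95% limits: 0.0588 to 0.1849 (rivaroxaban) and 0.0229 to 0.1185 (aspirin).
- Newcombe lower limit: 0.0532 − √[(0.1064 − 0.0588)² + (0.1185 − 0.0532)²] = 0.0532 − 0.0808 = −0.028.
- Newcombe upper limit: 0.0532 + √[(0.1849 − 0.1064)² + (0.0532 − 0.0229)²] = 0.0532 + 0.0841 = 0.137.
- Risk ratio 2.0, score 95% interval 0.74 to 5.4.

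For 4 vs 2 patients, p = 0.68, the difference is +2.1 points (−3.8 to +8.5) and the risk ratio is 2.0 (0.44 to 9.2). Both results are non-significant, and both leave room for a several-fold increase.

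**The case against.** A reader might infer that the trial will present a non-significant bleeding result as evidence of safety. The documents do not say so. They set no non-inferiority margin, make no such claim and give no interpretation rule. Protocol 2.5 is a justification written before the trial, and the bleeding test is not planned to support it. The risk-benefit objective is a few words in SAP 2.3.3 that do not appear in the protocol's own exploratory objective. What stands is narrower: the plan leaves the interpretation open and supplies no bound.

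A reader might also take a particular miss rate as a property of this trial. It is not, because the documents give no bleeding rate. The definition of clinically relevant non-major bleeding is broad, and total bleeding adds minor events, so risks above 10% cannot be excluded for that row. Nor is doubling a documented expectation: the factor of 2 in Protocol 2.5 is for rivaroxaban combined with aspirin, whereas this trial compares rivaroxaban alone with aspirin.

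The unshown z-test p-values should not be over-read either. That rule covers variables with more than two categories. It could reach bleeding, because SAP 4.7.3 puts each patient in one of several severity classes, but it does not fit the adverse event rows. Tables 7.8.3 and 7.8.4 do show a p-value, and it is these tables that carry the point.

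Finally, counts by arm are tabulated, so anyone can work out the intervals later. A data and safety monitoring board reviews safety, and the protocol calls the trial exploratory. Low power for harms is ordinary in such a trial and is not itself an error. All of this limits the weight of the point. It does not explain why compliance and pulse rate have planned intervals and bleeding has none.

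**Conclusion.** The gap is real and can be read directly from SAP 6.3 and tables 7.8.3 and 7.8.4: the between-arm comparison of bleeding and adverse events rests on a p-value, with no effect estimate and no confidence interval. On the assumptions used (94 dosed patients per arm, Fisher's test, a hypothetical doubling), the chance of a non-significant result runs from 99.5% at an aspirin-arm risk of 1% to 18% at 20%. The test is therefore uninformative for rare events such as major bleeding and becomes reasonably sensitive only if bleeding is common. That range illustrates why an interval is needed; it does not predict this trial's result. This is an inexpensive improvement in reporting, worth making because it concerns the main risk the protocol names.

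**What to change.** In SAP 6.12.3 and 6.12.4, and in the patient-level rows of tables 7.8.3 and 7.8.4 (AE, SAE, ADR, SADR; major, CRNM, minor and total bleeding), add the risk difference (rivaroxaban minus aspirin) and the risk ratio, each with a 95% confidence interval. Name the methods, for example Newcombe for the difference and score for the ratio. The event-count rows need no such columns.

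Add a sentence that safety conclusions on bleeding rest on the estimate and its interval, and that p > 0.05 alone will not be reported as absence of increased bleeding. If the Fisher p-value is kept, say which result leads, because the two can disagree near the boundary: 19 vs 9 patients gives p = 0.064, while the Newcombe interval is +0.4 to +20.9 points and the score interval for the ratio is 1.03 to 4.4.

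The cost is two extra columns in two tables and a few lines of SAP text, with no further patients or data. The drawback for the sponsor is that the intervals will be wide and the safety statement less favourable.

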#### 6.4 Subject Disposition

Subject disposition analyses will be based on all enrolled subjects. The following summaries will be provided:

 Subject disposition, as the number of subjects screened, randomized and completed treatment will be summarized.

The following listings will be provided:

- Listing of subjects withdrawn or dropped out: date of baseline visit, date of the last visit, discontinued by reason
- If there are any protocol deviations, including violation of inclusion/exclusion criteria, and postenrollment deviations which will impact assessment of efficacy and safety endpoints, a listing will be generated.

#### 6.5 Demographics

Demographic characteristics will be summarized in total and by treatment groups (and center) on the basis of FAS, PPS and SAF. Listings of demographic characteristics will be presented.

#### 6.6 Medical History

Medical history will be summarized for FAS, PPS and SAF by each treatment group. Frequency tables will be provided for pregnancy test and ECG results.

#### 6.7 Concomitant medication and Acute Diseases

Medications taken will be recorded from the day of informed consent until the EOT visit (day 0-week 52). Patients who received a concomitant medication at any point of time will be counted in the category "yes". All patient who did not receive any concomitant medication in the course of the study will be counted in the category "no". Number and proportion of subjects taking prior/concomitant medication will be summarized.

#### 6.8 Compliance

The overall treatment compliance will be calculated as: [1- (overall amount of drug dispensed – overall amount of drug returned) / (overall amount of drug dispensed)]x 100%.

In addition to the overall compliance, the treatment compliance will be presented by the following specific ranges for each treatment group: <50%, <80%. Analysis of compliance will be based on FAS.

#### 6.9 Treatment exposure and observation period

The duration of treatment exposure period during the study is calculated as:

(last drug administration date – first drug administration date) + number of days to next visit after last drug administration.

The duration of observation period during the study is calculated as:

last contact date - randomization date +1.

The duration of exposure and the duration of observation period will be summarized for each treatment group (FAS, PPS and SAF).

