#### 4.2.1 Treatment groups

#### TABLE 1: TREATMENT GROUPS

7 study visits will be performed during the study. Subjects are obliged to come to the study center for 5 visits. Visits will take place at week -2 (screening - V0), day 0 (randomization/baseline - V1), at week 2 (V2), 4 (V3), 8 (V4), 12 (safety/compliance - V5) and week 20 (end of treatment for the first study period with vascular function test - V6).). Visit 3 and Visit 5 will be conducted as a telephone visit.

Additionally, 80 patients of the study population will perform 7 additional visits during the extension period. These visits will start after week 20. Patients attending the extension period will perform overall 14 study visits for 8 of these visits they will come to the study center whereas overall 6 visits are performed as telephone visits. The additional visits will take place at week 24

(V7), week 28 (V8), week 32 (V9), week 36 (V10), week 40 (V11), week 44 (V12) and week 52 (end of treatment extension - V13). Visit 7, 9, 11 and 12 will be conducted as a telephone visit. Measurements of FBF, LDF and pletysmography at baseline-visit, visit week 20 (V6) and EOT-visit (V13) can be done up to 3 days after the visits in the corresponding study location that provides these measurements. Patients will be informed of the procedure by the physician.

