## 5.7 Dispensing of IMP

All packages should be inspected visually before distribution to the study subjects. The IMP will be dispensed to the subjects during the following visits by the site personnel. Each subject will get the following amounts of the randomized IMPs.

Visit Week	V0 day28	V1 day 0 ±4d	V2 2 ±2d	V3( тv) 4 ±2d	V4 8 ±2d	V5( тv) 12 ±2d	V6 20 ±2d	Dispensed medication
Rivaroxa- ban	-	90 Tabl. (3 Packs)	210 Tabl. (7 Packs)	-	330 Tabl. (11 Packs)	-	270 Tabl. (9 Packs)	630 (+270) Tabl. = 21 (+9) Packs
Aspirin	-	50 Tabl. (1 Pack)	50 Tabl. (1 Pack)	-	50 Tabl. (1 Pack)	-	100 Tabl. (2 Packs)	150 (+100) Tabl. = 3 (+2) Packs

 TABLE 9: DRUG DISPENSE FOR FIRST TREATMENT PERIOD (1 PACK RIVAROXABAN CONTAINING 30 TABLETS; 1 PACK ASPIRIN CONTAINING 50 TABLETS);

Visit Week	V7 (TV) 24 ±2d	V8 28 ±2d	V9 (TV) 32 ±2d	V10 36 ±2d	V11 (TV) 40 ±2d	V12 (TV) 44 ±2d	V13 52 ±2d	Dispensed medication
Rivaroxa- ban	-	210 Tabl. (7 Packs)	-	510 Tabl. (17 Packs)	-	-	-	720 Tabl. = 24 Packs
Aspirin	-	50 Tabl. (1 Pack)	-	150 Tabl. (3 Packs)	-	-	-	200 Tabl. = 4 Packs

OPTIONAL: DISPENSE OF IMP AT V6 FOR PATIENTS PARTICIPATIONS TO EXTENDED TREATMENT PERIOD

TABLE 10: DRUG DISPENSE FOR EXTENDED TREATMENT PERIOD (80 OF 188 PATIENTS) (1 PACK RIVAROXABAN CONTAINING30 TABLETS; 1 PACK ASPIRIN CONTAINING 50 TABLETS)

The dispensing of IMP will be recorded in the drug accountability log in the ISF according to provided templates.

Study subject will receive a medication diary for documentation of intake.

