## 5.9 Selection of dosage of IMP and frequency of treatment

Rivaroxaban will be administered at a dose of 5 mg ( $2 \times 2.5$  mg) twice daily (each 12 h), aspirin will be administered at a dose of 100 mg once daily (each 24 h).

The first dose of either study drug will be administered to the participants at the day of randomisation (visit 1). Further administrations take place at Visit 2 (after 2 weeks) and visit 4 (after 8 weeks).

Rivaroxaban will be administered according to the described instructions. Dosage and frequency of aspirin treatment applied in this study will follow the general specifications of the given SmPC. For patients participating in the extended treatment period, drug dispense will additionally take place at visit V6 (after 20 weeks), at visit V8 after 28 weeks and at visit V10 after 36 weeks.

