Both substances have a wide therapeutic window. Therefore, in case of asymptomatic overdosing without overt bleeding complications no specific treatment actions need to be taken and patient should be kept under surveillance. For rivaroxaban, gastrointestinal uptake can be reduced by activated carbon application within 3 h after intake of rivaroxaban, the same is applicable for aspirin. Aspirin might be removed from the circulation by hemodialysis. No specific antidot is available for either drug. In case of bleeding complications study treatment should be interrupted and symptomatic therapy (fluid resuscitation and blood transfusion as well as mechanical measures to control bleeding) should be initiated immediately. In the case of aspirin further bleeding can be prevented by platelet transfusion. In the case of rivaroxaban therapy with prothrombin complex or recombinant factor VIIa should be considered.

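### The exposure formula in SAP 6.9 runs to the next visit, not to the last intake, so it misstates time on drug for early stoppers and weakens the arm comparison in table 7.5

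*SAP*

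**What the plan says.** SAP 6.9 builds exposure from two terms. The first is "last drug administration date – first drug administration date"; the second, added to it, is the "number of days to next visit after last drug administration". Observation time is a separate quantity, "last contact date - randomization date +1". Both are summarised by arm in the FAS, PPS and SAF, and mock table 7.5 gives each a group comparison with effect, p-value and 95% CI.

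The SAP defines neither drug administration nor next visit. Protocol 5.9 places the first dose at visit 1 and continues: "Further administrations take place at Visit 2 (after 2 weeks) and visit 4 (after 8 weeks". Those are the visits at which drug is handed out. For the extension it adds dispensing at week 20, "at visit V8 after 28 weeks and at visit V10 after 36 weeks".

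The schedule in Protocol 4.2.1 has visits that follow a hand-out but are only telephone contacts. After the week 8 hand-out the next two are "12 (safety/compliance - V5) and week 20 (end of treatment for the first study period". V5 (week 12) is by telephone. So are V11 (week 40) and V12 (week 44), which follow the week 36 hand-out.

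On intake and interruptions, Protocol 5.7 says "Study subject will receive a medication diary for documentation of intake", and Protocol 5.11.1 says "In case of bleeding complications study treatment should be interrupted".

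**The concern.** An exposure measure should end when the patient stops taking the drug. This one ends at a visit, and the stop date at most decides which visit. Time off drug between the stop and that visit is counted as time on drug, and an interruption leaves no trace.

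The bleeding and adverse event tables (SAP 7.8.3 and 7.8.4) show numbers of patients and events without time at risk. The exposure summary is the only one of time on drug to set beside them. The trial is open-label, and Protocol 2.5 names bleeding as the major risk of anticoagulation, so stopping could differ between arms. In that case the summary and its p-value in table 7.5 would understate the difference.

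**Working it through.** **Algebra.** (last − first) + (next visit − last) = next visit − first. The last administration date drops out.

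**Inputs.** Hand-outs at weeks 0, 2 and 8, then 20, 28 and 36 in the extension (Protocol 5.7 and 5.9). On-site visits at weeks 0, 2, 8, 20, 28, 36 and 52; telephone visits at weeks 4, 12, 24, 32, 40 and 44 (Protocol 4.2.1). Planned duration 20 weeks, or 52 with the extension.

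**Four readings.** The planned duration is the figure to reproduce for a completer. The last column takes a main-period patient who stops on day 60 (true exposure about 60 days). Week 8 is day 56, week 12 day 84 and week 20 day 140.

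| Administration | Next visit | Completer, main / extension (weeks) | Stop on day 60 |
|---|---|---|---|
| Hand-out | On-site | 20 / 52 | 56 + 84 = 140 days |
| Hand-out | Any, incl. telephone | 12 / 40 | 56 + 28 = 84 days |
| Intake | On-site | 20 / 52 | 60 + 80 = 140 days |
| Intake | Any, incl. telephone | 20 / 52 | 60 + 24 = 84 days |

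The intake rows assume that a completer's last intake falls at V6 or V13. A result of 140 days is 80/60 = 133% too high, and 84 days is 24/60 = 40% too high. The second row also under-counts completers by 8 weeks (main period) or 12 weeks (extension).

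**Largest over-credit, hand-out and on-site reading** (patient stops just after the hand-out):

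| Last hand-out (week) | 0 | 2 | 8 | 20 | 28 | 36 |
|---|---|---|---|---|---|---|
| Next on-site visit (week) | 2 | 8 | 20 | 28 | 36 | 52 |
| Over-credit (weeks) | 2 | 6 | 12 | 8 | 8 | 16 |

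The intake and on-site reading has the same maxima. With intake and any visit, the longest gap is 8 weeks (week 12 to 20, or 44 to 52).

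**Arm differences, on-site reading.** The documents give no stopping rates by arm and no stop times, so these are assumptions. Stop times are taken as uniform, and stoppers are credited to the next on-site visit.

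- Stops over weeks 0–20. The true mean shortfall against 20 weeks is 10. The formula's shortfall is 18 for stops in weeks 0–2 (probability 0.1), 12 in weeks 2–8 (0.3) and 0 in weeks 8–20 (0.6): 1.8 + 3.6 + 0 = 5.4. So 5.4/10 = 54% of a true difference survives. With 25% against 10% stopping, the true difference is 0.15 × 10 = 1.50 weeks and the formula gives 0.15 × 5.4 = 0.81.
- Stops over weeks 0–8. True shortfall 16; formula 0.25 × 18 + 0.75 × 12 = 13.5. The difference is 2.40 weeks true and 2.025 by formula (84% survives).
- Stops over weeks 8–20. True shortfall 6; formula 0. The difference is 0.90 weeks true and 0 by formula.
- Extension, stops over weeks 20–52. True shortfall 16; formula 0.25 × 24 + 0.25 × 16 + 0.5 × 0 = 10, so 62.5% survives. For stops in weeks 36–52 none survives.

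**No next visit.** Protocol 4.8.2 defines a dropout as someone who discontinues study participation, and Protocol 9.1.8 plans for 25% of them. For those with no later visit the second term does not exist, and the SAP gives no substitute.

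**The case against.** The strongest defence is that the formula has a tolerable reading. If administration means intake and telephone visits count, completers get 20 and 52 weeks and no stopper gains more than 8 weeks. Early stops also show elsewhere: SAP 6.4 lists withdrawn subjects with last visit date and reason, the AE listings in SAP 6.12.3 carry the action taken, and observation time is reported separately. No sample size, primary test or efficacy result depends on exposure.

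Most of this stands, and it limits the point. It does not rescue the rule. Even the kindest reading counts 24 days off drug as exposure in the day-60 example and has no value for a patient who does not return. Listings do not correct a summary or its p-value. Compliance is no check either: the SAP 6.8 formula as printed reduces to returned over dispensed, the opposite of the quantity described in SAP 4.4.

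A reader might infer four stronger things that the documents do not support.

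- *Early stoppers typically gain 12 to 16 weeks.* Those are extremes. They need next visit to mean on-site visit and a stop just after the week 8 or week 36 hand-out.
- *Arm differences in exposure disappear.* In general they shrink. On the on-site reading they vanish only when the stops fall in weeks 8–20 or 36–52. Nor can the planned 25% dropouts all be assumed to attend V6, since by definition they leave the study.
- *Bleeding rates per unit of exposure are biased.* The SAP plans no such rate. Bleedings and adverse events are compared as proportions of patients.
- *The true dates are already in the database.* The AE action field holds categories without dates. A diary is issued, but the source-data list in Protocol 7.1.2 does not name it, and neither document says that it is entered in the eCRF.

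**Conclusion.** Wrong as written. Under every reading the SAP 6.9 rule misstates exposure for early stoppers, completers or both. It ignores interruptions and is undefined where no later visit exists. The 12-week and 16-week maxima, and the loss of arm differences worked out above, rest on the on-site reading; the surviving shares also rest on the assumed uniform stop times and on stoppers being credited to that visit. The effect is confined to the exposure summary and its comparison in table 7.5. That makes it worth correcting before analysis, because nothing else in the plan summarises time on drug beside the safety counts.

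**What to change.** Replace the SAP 6.9 exposure formula with: exposure = last intake date − first intake date + 1, less documented interruption days. Drop the days-to-next-visit term.

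Take the last intake date from the medication diary or from a recorded stop date. If neither is available, estimate days on drug from tablets dispensed minus tablets returned, which SAP 4.4 says will be recorded. Divide by the daily tablet count stated in Protocol 5.2 and 5.3 (four for rivaroxaban, one for aspirin), and cap the result at the last contact date. Tablet counts already leave out days without drug, so interruptions should not be subtracted again under the fallback. Report by arm how many patients needed it.

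Keep the observation-period formula and show both durations in table 7.5 as planned. The cost is SAP wording, programming and some date cleaning for patients who stop early. Whether diary dates are captured electronically should be checked first, because that decides how often the fallback is used.
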